3. Specific Aim 3 (Secondary Aim): To determine the efficacy of Vortioxetine in reducing depressive symptoms in PTSD patients.

Hypothesis: PTSD patients randomized to acute therapy with Vortioxetine will show more improvement in depressive symptoms compared to subjects randomized to placebo, as determined by mean changes in the Montgomery-Asberg Depression Rating Scale (MADRS) score over the course of 12 weeks.

4. Exploratory Aim 1: Startle: To assess fear potentiation, conditional discrimination (AX+/BX-), and fear inhibition using acoustic startle methodology in a classical conditioning paradigm in PTSD patients before and after treatment with Vortioxetine.

Hypothesis: PTSD subjects randomized to 12 weeks of Vortioxetine will have improved fear inhibition as measured by the AX+/BX- paradigm compared to baseline, while placebo subjects will not show improvement.

5. Exploratory Aim 2: Cognition, Functional Capacity, and Quality-of-Life: To assess neurocognitive performance (pre- and post-treatment) with tests shown to be sensitive to PTSD (e.g. learning and memory, concentration and attention, and executive functioning). In addition, to explore performance-based measures of everyday living skills, and measure quality-of-life as indexed by subjective reports.

Hypothesis: Statistically significant changes detected for these variables will be correlated across domains.

6. Exploratory Aim 3: Genotyping and Gene Expression: To explore whether response to Vortioxetine is associated with certain candidate gene polymorphisms previously associated with PTSD, and whether treatment with Vortioxetine alters gene expression patterns differentially in treatment responders and non-responders.

Hypothesis: Polymorphisms of specific candidate genes previously identified as relevant to PTSD will be differentially distributed between responders and non-responders to vortioxetine.

III. SIGNIFICANCE/BACKGROUND

Significance of PTSD and Limitations of Current Pharmacotherapies

PTSD is a common chronic anxiety disorder that is often debilitating and follows exposure to an overwhelming traumatic event. PTSD occurs in approximately 8%-14% of the U.S. population (Breslau et al 1998; Davidson et al 1991; Kessler et al 1995). Rates of PTSD among women in the US are higher than in men being approximately twice that of men 12%-18% (Breslau et al 1998; Resnick et al 1993).

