3) Study period II Treatment (Day 0 to 84): Visits 2 through 9. This is the 12-week period of double-blind placebo-controlled acute treatment. At day 0, EKG for safety monitoring will be conducted. The baseline mRNA sample will be collected. All subjects who continue to meet eligibility criteria will be randomized to one of two groups: Vortioxetine or placebo. Randomization will be performed at a 1:1 ratio into two treatment groups, and both vortioxetine and placebo will be distributed to the patient in blister packs. If a participant is taking 10mg of vortioxetine they will be provided with 2 blister packs at each visit. If a participant is taking 20mg, they will be provided with 4 blister packs. Surrogate marker testing for psychophysiology, mRNA, and neuropsychological testing will be repeated at the completion of the double-blind treatment. Due to the amount of study procedures for certain study visits, we will allow study visits to be done over two days.

4) Follow-Up (Day 84 to 98): Visit 10. Patients will return to the clinic two weeks after the last dose of study medication for assessment of psychiatric status, suicidality, follow-up of any abnormal laboratory or EKG results, and to assist with transition of psychiatric care, if indicated.

See the **Schedule of Events** chart at the end of this section for details of the procedures performed during each visit.

B. Justification of Sample Size

Power Analysis:

Samples of n=60 (2 groups) are associated with reduced but adequate power. Between group differences in change scores of $d=.70$ are detectable with .80 power at $p<.05$. Correlations of

.33 between two variables are detectable with power=.80 in the full sample of 60. Within treatment conditions (n=30) correlations of $r=.50$ are detectable with the same level of power.

C. Informed Consent, Regulatory and Ethical Considerations

The study will be conducted in accordance with Good Clinical Practices (GCP), 21CFR Parts 50 and 56 and all applicable regulatory requirements. Approval for conduct of the study will be obtained from the institutional review boards at both sites.

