2a. At the start of the study, participants will undergo specific laboratory tests, as outlined in the Schedule of Events above. Blood tests include: complete blood cell count (CBC) with differential, thyroid functioning (TSH), and free thyroxine, fasting blood sugar, liver function tests (LFTs), including total bilirubin, a hepatitis panel, and a serum pregnancy test in women of child-bearing potential. Participants also undergo a urine toxicology screen, urine pregnancy test and urinalysis testing. Additional blood or urine tests for disallowed medications or drugs of abuse may be performed during the randomization phase at the discretion of the investigator.

3. Pharmacokinetics Testing

3a. As outlined in the schedule of events, participants will undergo confirmatory laboratory testing at visits 5, 7, and 9. Blood will be drawn and tested to confirm the level of Vortioxetine in the participant's system at the time of their study visit.

J. Exploratory Biological and Neuropsychological Assessments

In addition to the treatment outcome goals, we will examine previously identified genetic risk factors for predictors of treatment response. We will also examine SNPs associated with PTSD which meet genome-wide significance within an ongoing cross-sectional n=8000 Genome Wide Association Study.

Hypothesis 1: Based on our extensive prior experience in examining physiological markers of fear responding, we hypothesize that trauma-exposed individuals with PTSD will exhibit a higher likelihood of responding to PTSD treatment if they display differential physiological signatures of PTSD (e.g. increased dark-enhanced startle and decreased extinction of fear), compared to those without these physiological signatures of PTSD.

Hypothesis 2: Based on our previous work in PTSD identifying significant cognitive and functional capacity deficits, we hypothesize that treatment of with vortioxetine will improve cognitive and functional capacity.

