1. DNA

We will draw DNA on all consenting subjects to evaluate whether carriers of identified risk alleles are associated with response or non-response to voritoxetine.

2. mRNA

We will draw 12 mls of blood at baseline and at week 12 to evaluate the expression of HPA-related mRNA expression.

3. Neurophysiology: Startle Testing

3a. Conditioning sessions. The following methods will allow us to assess fear acquisition, and conditional discrimination (learned safety), as well as the subjects' awareness of reinforcement contingencies in the experiment. The aversive stimulus (US) in these studies will be a 250 ms airblast with an intensity of 80 p.s.i. directed to the larynx as described in similar human fear conditioning studies (Grillon & Davis, 1997; Jovanovic et al. 2005). A compressed air tank connected to polyethylene tubing and controlled by a solenoid switch will emit the airblasts. The conditioned stimuli (CS's) used in the AX+/BX- session (A, B, C and X) will be different colored shapes; in the fear acquisition and extinction sessions the CS's will be neutral pictures. The CS's will be presented on a computer monitor. The pictures and colored shapes will be counterbalanced across subjects. The stimuli will be presented using SuperLab 3.0 for Windows (Cedrus, Inc.) and synchronized with the psychophysiological data acquisition using a DIO card (Measurements Computing, Inc). The psychophysiological data will be collected with Biopac MP150 (Biopac Systems, Inc.). Skin conductance will be acquired concurrently with acoustic startle.

3b. Acoustic startle. The acoustic startle response (eyeblink component) will be measured via electromyography (EMG) of the right *orbicularis oculi* muscle. Two 5 mm Ag/AgCl pre-gelled disposable electrodes will be positioned approximately 1 cm under the pupil and 1 cm below the lateral canthus. All resistances will be less than 6 kilo-ohms. EMG activity is acquired at a sampling rate of 1kHz, amplified and digitized. The startle probe (noise burst) will be a 108-dB [A] SPL, 40-ms burst of broadband noise with a near instantaneous rise time.

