Multiple outcome measures: To address the possible increase in Type I errors due to multiple outcome variables, we have a priori selected a single outcome measure (CAPS total) which will maintain the significance level (α) 0.05 for the primary analysis. For secondary outcome measures, we will adjust p-values by controlling for the false discovery rate (Benjamini & Hochberg, 1995) and report both unadjusted and adjusted p-values.

Random effects: Given that the majority of outcomes are behavioral in nature, we expect that there will be significant individual level variance that will need to be incorporated into the model. Thus our overall analysis approach will be to use linear 2-level mixed models or generalized linear mixed models, as appropriate, to analyze the repeated measures data with at least a random intercept to incorporate individual level variation. We will also incorporate a random slope if necessary however, it is not always necessary in our experience, particularly with scales with a limited range such as MADRS.

VIII. HUMAN SUBJECTS

Updated January 22, 2019

A. Subject Recruitment

Men and women between the ages of 18-65 with a primary diagnosis of PTSD using the DSM-V criteria will be eligible for the study. A total of 60 subjects will be randomized (30 to Vortioxetine and 30 to placebo). These subjects will be enrolled at 2 sites, Emory University School of Medicine and Miami Miller School of Medicine. Subjects will enter this study having been recruited through referrals from outpatient clinics, or referrals from other community clinics and community clinicians (psychiatrists, psychologists, and social workers) in the greater Atlanta and Miami regions. In addition, we will advertise locally in newspapers and radio and will post recruitment messages on internet sites.

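### The biomarker predictor hypotheses are set against a yes/no responder label, for which the plan states no power; a continuous CAPS-5 outcome would retain more of it

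*Combined protocol and SAP*

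**What the plan says.** **Predictor hypotheses.** All are in the combined protocol and SAP.

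- Section V.J, Hypothesis 1 (startle): trauma-exposed patients with PTSD "will exhibit a higher likelihood of responding to PTSD treatment if they display differential physiological signatures of PTSD", "compared to those without these physiological signatures of PTSD". Two examples of a signature are given, in graded terms (more dark-enhanced startle, less fear extinction), but no threshold.
- Section II, Exploratory Aim 3 (genotype): candidate polymorphisms "will be differentially distributed between responders and non-responders to vortioxetine".
- Section V.J.1 (DNA): the question is whether "carriers of identified risk alleles are associated with response or non-response".
- Section V.J, Hypothesis 3: risk-allele carriers are compared with non-carriers on likelihood of response. mRNA and methylation are named as predictors of response, with no cut-off.

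**Response.** Specific Aim 2 defines it as a composite: at least 30% improvement in CAPS-5 together with a CGI-I of 1 or 2.

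**Power.** Section V.B gives two figures for associations. One is a correlation of .33 in the full sample of 60 at power .80. The other reads: "Within treatment conditions (n=30) correlations of $r=.50$ are detectable with the same level of power". It names neither an aim nor a biomarker. It states no power for a binary response.

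**Analysis.** Section VII.B fits continuous variables with PROC MIXED and categorical ones with gllamm, and allows covariates as main effects in response-based analyses. It names no test for the biomarker hypotheses.

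**Data.** The Schedule of Events collects CAPS-5 at weeks 0, 2, 4, 8 and 12. Startle is recorded as an EMG response (V.J.3b).

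**The concern.** Turning a graded improvement score into responder/non-responder throws away information about how much each patient improved. With 30 patients per arm there is little to spare. The only association power in the plan is for correlations, so a reader may carry the .80 over to the responder comparisons, where it does not apply. A marker with a real association of the size V.B calls detectable could then be missed much more often than expected, and the null result read as evidence that the marker does not predict outcome.

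The startle hypothesis adds a second problem. A signature with no stated cut-off leaves room to choose one after the data are seen.

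**Working it through.** **Inputs.** r = .50 with n = 30, r = .33 with n = 60, and alpha .05 come from V.B. Sidedness is not stated, so two-sided is used first. Section VIII.A gives 30 patients per arm.

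**Assumptions not in the documents.** Marker and CAPS-5 change are bivariate normal; there is no dropout; response is a cut of CAPS-5 change; the response rate p is 30-60%. The abstract says only that SSRI response rates rarely exceed 60%.

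**Step 1: reproduce V.B.** Power = Φ(atanh(r)·√(n−3) − 1.960).

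- r = .50, n = 30: 0.549 × 5.196 − 1.960 = 0.894, so power is .81. Simulation gives about .83. This agrees with the stated .80.
- r = .33, n = 60: 0.343 × 7.550 − 1.960 = 0.628, so power is .735. Simulation gives about .74. This is short of the stated .80; two-sided, .80 needs about 70 patients or r of about .355. One-sided power is .83.

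**Step 2: dichotomise the outcome only.** The correlation shrinks to r_pb = r·φ(z_p)/√(p(1−p)), where z_p is the standard normal quantile of p.

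- p = .50: the factor is .3989/.5 = .798.
- p = .30: the factor is .3477/.4583 = .759.

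| Case | r_pb | Power, formula | Power, simulated t-test by response group |
|---|---|---|---|
| r = .50, n = 30, p = .50 | .399 | .593 | .62 |
| r = .50, n = 30, p = .30 | .379 | .546 | .56 |
| r = .33, n = 60, p = .50 | .263 | .530 | .55 |
| r = .33, n = 60, p = .30 | .250 | .489 | .50 |

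Over p = 30-60% and both methods, power is about .55-.63 for r = .50, n = 30 (from about .83). For r = .33, n = 60 it is about .48-.55 (from about .74).

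One-sided testing does not remove the loss. For r = .33, n = 60, power goes from .83 to about .62-.68.

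**Step 3: dichotomise startle as well (conditional).** Assume further that 30-50% of patients have the signature and that a 2×2 table is tested. With both halves at 50% and r = .50, the response rates are .667 with the signature and .333 without, and power at n = 30 is .44. Over the range:

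- r = .50, n = 30: .35-.44 (Pearson chi-square) or .27-.34 (Fisher exact).
- r = .33, n = 60: about .27-.39 over both tests.

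For r = .50, such a table would need about 70-84 patients for .80 power.

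**Step 4: genotype.** Carrier status is binary by nature, so only the outcome dichotomy can be avoided. With a carrier/change correlation of .50, n = 30 and 30-50% carriers, power is about .83-.86 against CAPS-5 change and roughly .47-.70 against the responder label.

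**The case against.** Four points on the other side carry weight.

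1. **V.B is not tied to the biomarkers.** A reader might infer that its correlations were offered as the power for the responder tests and are therefore wrong. The text does not say so. It speaks of two variables, and Exploratory Aim 2 itself predicts correlations across domains, so the figures have another natural use. What stands is that no power is given for the responder comparisons.

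2. **No median split or 2×2 test is planned.** A reader might infer from Hypothesis 1 that power falls to about .3. That needs a dichotomised startle variable and a table test, and neither is specified. Section VII.B points to regression-type models, in which a startle score can stay continuous. Step 3 is therefore conditional; Step 2 is not affected by this point.

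3. **The continuous data are not shown to be discarded.** CAPS-5 total is the primary outcome in mixed models, Exploratory Aim 1 uses startle before and after treatment, and section III speaks of moderators and mediators of outcome. The narrower statement holds: the genotype and startle predictor hypotheses are worded against response, and no continuous outcome is named for them.

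4. **Response is a legitimate endpoint and is not simply a cut of CAPS-5 change.** It uses percentage change and also requires CGI-I of 1 or 2. The calculation thresholds CAPS-5 change alone, so it illustrates the loss and does not measure it for the composite. Exploratory Aim 3 also uses responder status as a grouping factor for gene-expression change, where CAPS-5 change cannot simply take its place. This limits the remedy: the responder analyses should stay.

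**Conclusion.** The point holds for the outcome. The predictor hypotheses are framed on a binary response, the plan gives no power for that, and a graded measure of improvement is already collected. Under the stated assumptions, the binary outcome alone costs roughly 20 to 28 percentage points of power (.83 to .55-.63) at r = .50, n = 30, and roughly 19 to 26 points (.74 to .48-.55) at r = .33, n = 60. The figure of about .25-.45 applies only if the startle signature is analysed as present/absent, which the documents leave open.

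The sizes rest on normality, the assumed response rate, no dropout, and treating response as a cut of CAPS-5 change. The loss for the actual composite cannot be derived from the documents. Only exploratory analyses are affected; the primary and secondary results are not. This is a cheap improvement, not a flaw that threatens the trial.

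**What to change.** - In Exploratory Aim 3 and V.J (Hypotheses 1 and 3, and V.J.1), name Week 12 CAPS-5 change, continuous and adjusted for baseline CAPS-5, as the main outcome of the predictor analyses.
- Enter startle, mRNA and methylation as continuous scores, and genotype as carrier status. If a present/absent startle signature is wanted as well, define its cut-off before the data are examined.
- Keep the responder/non-responder comparisons as supporting analyses, including the Aim 3 comparison of gene-expression change by responder status.
- State in V.B that the correlation figures apply to continuous-by-continuous analyses and not to the responder comparisons.

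The cost is wording only, with no new visit, assay or patient. There is one small downside: the main predictor result would then concern degree of CAPS-5 improvement and not the composite response that includes CGI-I. Keeping the responder comparisons as support covers that.

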1. DNA

We will draw DNA on all consenting subjects to evaluate whether carriers of identified risk alleles are associated with response or non-response to voritoxetine.

2. mRNA

We will draw 12 mls of blood at baseline and at week 12 to evaluate the expression of HPA-related mRNA expression.

3. Neurophysiology: Startle Testing

3a. Conditioning sessions. The following methods will allow us to assess fear acquisition, and conditional discrimination (learned safety), as well as the subjects' awareness of reinforcement contingencies in the experiment. The aversive stimulus (US) in these studies will be a 250 ms airblast with an intensity of 80 p.s.i. directed to the larynx as described in similar human fear conditioning studies (Grillon & Davis, 1997; Jovanovic et al. 2005). A compressed air tank connected to polyethylene tubing and controlled by a solenoid switch will emit the airblasts. The conditioned stimuli (CS's) used in the AX+/BX- session (A, B, C and X) will be different colored shapes; in the fear acquisition and extinction sessions the CS's will be neutral pictures. The CS's will be presented on a computer monitor. The pictures and colored shapes will be counterbalanced across subjects. The stimuli will be presented using SuperLab 3.0 for Windows (Cedrus, Inc.) and synchronized with the psychophysiological data acquisition using a DIO card (Measurements Computing, Inc). The psychophysiological data will be collected with Biopac MP150 (Biopac Systems, Inc.). Skin conductance will be acquired concurrently with acoustic startle.

3b. Acoustic startle. The acoustic startle response (eyeblink component) will be measured via electromyography (EMG) of the right *orbicularis oculi* muscle. Two 5 mm Ag/AgCl pre-gelled disposable electrodes will be positioned approximately 1 cm under the pupil and 1 cm below the lateral canthus. All resistances will be less than 6 kilo-ohms. EMG activity is acquired at a sampling rate of 1kHz, amplified and digitized. The startle probe (noise burst) will be a 108-dB [A] SPL, 40-ms burst of broadband noise with a near instantaneous rise time.

3c. Response keypad. To assess subject awareness and US expectancy during each experimental session subjects will respond on a response keypad (SuperLab, Cedrus Corp.) in coordination with the EMG startle response monitoring system (SR-LAB, San Diego Instruments). During the fear conditioning sessions subjects will press a button marked "+" if they expect a CS to be followed by the US, a button marked "-" if they do not expect a CS to be followed by the US, and a button marked "0" if they are uncertain of what to expect.

3d. Skin Conductance Level. The skin conductance level will be acquired at a sampling rate of 1 kHz using the GSR module of the Biopac system. Two 5 mm Ag/AgCl disposable electrodes filled with isotonic paste will be attached to middle phalanges of the second and fourth finger of the non-dominant hand.

4. Neuropsychological Battery

4a. Rationale and Test Descriptions. Cognitive function will be assessed by Brief Assessment of Cognition in Schizophrenia (BAC-S) test battery with measures in: (1) list learning, (2) digit sequencing task, (3) token motor task, (4) verbal fluency, (5) tower of London test, and (6) symbol coding subtest. All BAC-S measures will be administered at specified time points, and the total composite z-scores will be compared to baseline total composite z-scores.

Updated January 22, 2019

4b. Performance Based-Measures of Functional Capacity

For the assessment of functional capacity, we will use instrumentation previously developed for use in schizophrenia: the UCSD performance-based skills assessment (UPSA; Patterson et al 2001). The UPSA is the most widely used functional capacity measure in serious mental illness, but suffers from a lengthy assessment format (30 minutes), high-level reliance on props, and geographic specificity. The UPSA-B involves role-play tasks similar in complexity to those that a community-dwelling person is likely to encounter. Administration requires an average of 10 minutes. The UPSA-B's two domains result in a summary score ranging from 0 to 100 and we will use the summary score as the dependent variable.

K. Clinical Care

1. Discontinuation from study

At the end of the treatment trial or when a patient discontinues the study prematurely, the efficacy evaluations will be repeated. In addition, a physical exam, 12-lead EKG, vital signs, weight, and laboratory measurements will be obtained. Patients will also be assessed for adverse experiences. All subjects who complete the trial or discontinue because of lack of response or side effects will receive treatment as clinically appropriate and will then be referred for appropriate follow-up care.

Patients may withdraw at any time, or may be withdrawn by the investigator should medical contraindications to the assigned medication develop, intolerable adverse reactions occur, or mood or anxiety worsens to an extent that, in the clinicians' judgment, further participation would put the patient at risk.

Pregnancy

The investigator will collect pregnancy information on any female subject who becomes pregnant while participating in this study. Any female subject who becomes pregnant while participating will be withdrawn from the study. The investigator will record pregnancy information on the appropriate form and submit it to [name] at the University of Miami (Email: [contact] [contact]) and to Takeda (Email: [name] iFax: [name]) within 24 hours of learning of a subject's pregnancy. The subject will also be followed to determine the outcome of the pregnancy. Generally, follow-up will be no longer than 6 to 8 weeks following the estimated delivery date. Any premature termination of the pregnancy will be reported. While pregnancy itself is not considered to be an AE or SAE, any pregnancy complication or elective termination of a pregnancy for medical reasons will be recorded as an AE or SAE. A spontaneous abortion is always considered an SAE and will be reported as such.

SAE Reporting

All SAEs will be reported to [name] and to Takeda within 4 calendar days of the site investigator becoming aware of the event. All fatal or life-threatening SAEs will be reported by facsimile within 24 hours. The appropriate SAE form will be completed and emailed or faxed to [name] and Takeda using the contact information listed in the Pregnancy section.

2. Suicide risk among patients treated with antidepressants

Subjects with major depressive disorder or with depression as part of bipolar disorder may experience worsening of their depression and/or the emergence of suicidal ideation and behaviour (suicidality), whether or not they are taking antidepressant medications, and this risk may persist until significant remission occurs. This guidance is consistent with global class

labelling for antidepressants. Although there has been a long-standing concern that antidepressants may have a role in inducing worsening of depression and the emergence of suicidality in certain subjects, a causal role for antidepressants in inducing such behaviours has not been established. Nevertheless, subjects being treated with study medication will be observed closely for clinical worsening and suicidality, especially at the beginning and end of the course of treatment, or at the time of dose changes, either increases or decreases. Consideration will be given to possibly discontinuing the investigational product in subjects whose depression is persistently worse or whose emergent suicidality is severe or abrupt in onset or was not part of the subject's presenting symptoms. To assess suicidal ideation and behaviors, the CSSRS will be used in this trial.

The following symptoms, anxiety, agitation, panic attacks, insomnia, irritability, hostility (aggressiveness), impulsivity, akathisia (psychomotor restlessness), hypomania, and mania, have been reported in patients being treated with antidepressants for major depressive disorder. Although a causal link between the emergence of such symptoms and either the worsening of depression and/or the emergence of suicidal impulses has not been established, consideration should be given to possibly discontinuing the investigational product in subjects for whom such symptoms are severe, abrupt in onset, or were not part of the subject's presenting symptoms.

2. Provision of Clinical Care

All subjects who complete the trial or discontinue the study because of lack of response or side effects will receive assistance in transitioning their care to another provider.

VII. DATA ANALYSIS AND STATISTICAL PLAN

A. Approach to Data Management

Case report forms are developed from adaptations of NIH and industry-funded clinical trial protocols in PTSD. Study data will be recorded on paper forms and translated to a digital format without specific patient identifying information. Patient identifiers will be maintained in a separate code book that will be kept in a locked cabinet in the Principal Investigator's office at each site. These data will be preserved on site with periodic monitoring by the primary site. At the end of the study, the databases for the different sites will be merged. Data will be entered sequentially and within a timely manner so that any queries for missing information can be resolved.

B. General Statistical Considerations

Possible risk factors/confounders: We expect the randomization procedure to equalize risk factors across treatment groups; however, we will produce summary statistics to explore any unexpected differences in the values of covariates in the treatment groups. While we do not expect differences in covariates in the treatment groups, it is very likely that the response groups will be different on some relevant clinical variables (e.g., comorbid conditions). However, these should affect only the analyses that include treatment response, and not analyses such as group-related change in CAPS. Thus, we will formally assess response group differences in possible covariates of interest and incorporate any covariates identified that are considered both statistically and clinically relevant as additional main effects for the response-based analyses. Specific types of interaction effects, such as effect modifiers specified a priori, will be the subject of exploratory analysis.

Site effects: Our assumption for the analysis plan and power calculations is that the protocols will be implemented sufficiently comparatively to avoid significant site effects in the results. Given that the randomization will be blocked by site, there is no reason to believe that the

subjects will have a different a priori probability of response or will be significantly different from a clinical perspective. However, we will test for site differences in all outcome measures with appropriate univariate comparisons to ensure that this is not a significant confounder. If there is evidence of significant site differences in response, we will proceed with stratified analyses in place of the proposed analyses.

Missing data: For those subjects randomized who do not complete treatment, an intent-to-treat approach will be implemented using linear and categorical mixed model methods. More specifically, all participants who are randomized to treatment group and have baseline measures will be included in the analysis. If the probability of a missing observation depends on either observed covariates in the model or the previous observations of the outcome variable (e.g. CAPS), these models will provide the correct conclusions (Little & Rubin, 2002). Any other missing data would be the result of incomplete recording of information or refusal of a subject to give information. Thus, the assumption that missing data are in fact missing at random (MAR), or that other variables under consideration will contain enough information to effectively model the outcome of interest, will be reasonable for these analyses.

Therefore, in the case of missing predictor variables, simple or multiple imputation methods (Little and Rubin, 2002) will be sufficient to provide “fill-in” methods so we can perform analyses of the full data set. All analyses described below will be performed on the complete data sets that result from this process. We will compare dropout patterns between groups and if there are concerns of informative dropout and/or informative intermittent missing data, we will perform sensitivity analyses to determine the effects of these assumptions on our main analyses (Molenberghs et al., 2004).

Analytic details: Continuous variables will be fit using SAS PROC MIXED, and categorical data will be fit using the gllamm add-on to Stata (Rabe-Hesketh et al; 2002). The gllamm method is preferred to SAS PROC GLIMMIX in that it is a full likelihood method which uses numerical integration for the random effects rather than a partial likelihood approximation. In addition, it provides empirical Bayes estimates of the random effects for model checking. Prior to model fitting, we will examine the distributions of the continuous outcome variables using visual inspection of histograms and boxplots to identify potential outliers. If variables are not normally distributed or contain outliers, then log transformations will be considered or appropriate nonparametric procedures will be substituted for the analyses stated.

Multiple outcome measures: To address the possible increase in Type I errors due to multiple outcome variables, we have a priori selected a single outcome measure (CAPS total) which will maintain the significance level (α) 0.05 for the primary analysis. For secondary outcome measures, we will adjust p-values by controlling for the false discovery rate (Benjamini & Hochberg, 1995) and report both unadjusted and adjusted p-values.

Random effects: Given that the majority of outcomes are behavioral in nature, we expect that there will be significant individual level variance that will need to be incorporated into the model. Thus our overall analysis approach will be to use linear 2-level mixed models or generalized linear mixed models, as appropriate, to analyze the repeated measures data with at least a random intercept to incorporate individual level variation. We will also incorporate a random slope if necessary however, it is not always necessary in our experience, particularly with scales with a limited range such as MADRS.

VIII. HUMAN SUBJECTS

Updated January 22, 2019

A. Subject Recruitment

Men and women between the ages of 18-65 with a primary diagnosis of PTSD using the DSM-V criteria will be eligible for the study. A total of 60 subjects will be randomized (30 to Vortioxetine and 30 to placebo). These subjects will be enrolled at 2 sites, Emory University School of Medicine and Miami Miller School of Medicine. Subjects will enter this study having been recruited through referrals from outpatient clinics, or referrals from other community clinics and community clinicians (psychiatrists, psychologists, and social workers) in the greater Atlanta and Miami regions. In addition, we will advertise locally in newspapers and radio and will post recruitment messages on internet sites.

Subjects will meet all inclusion/exclusion criteria outlined below. We will exclude subjects with history of bipolar disorder, psychosis, substance abuse or dependence that is current or existed 3 months prior to screening, history of borderline intellectual functioning or mental retardation, and clinically significant suicidal risk. We will exclude individuals with the following medical conditions, as evidenced by use of daily medications or prior treatment: cancer in past year, stroke, heart attack, angina, neurological disease (MS, epilepsy, Parkinson's), CNS lesions (head trauma), dementing illness, liver/kidney disease. The completion of self-report scales and cognitive tests requires a level of understanding that may not be present in those with low IQ. Medical illnesses and use of medication that may interfere with biological, and possibly psychological assessments, and current suicidality that requires immediate clinical intervention will be exclusionary for participation.

B. Inclusion/ Exclusion Criteria

Inclusion

CRITERION	METHOD OF ASCERTAINMENT
1. Males and Females between the ages of 18 and 65	History
2. Fulfills DSM-5 criteria for primary diagnosis of PTSD.	MINI
3. Willing and able to give consent	Clinical interview
4. A negative urine toxicology	Urine toxicology
5. For females of reproductive age, use of an effective birth control method* for the duration of the study or abstinence.	History
6. Duration of illness of PTSD for at least 3 months	History
7. An initial score at Screening, and Visit 2 (randomization) of ≥ 28 on the CAPS-5 for PTSD Studies	CAPS-5

